**Table 1: Estimated radiation for an adult patient: Study schedule compared to SoCa**

Visit		V1	V2	V3	V4	V5	V6	V7	V8	TOTAL
		Screening	IS	HD	W2	W6	M3	M6	M12	
Study protocol	X-Ray (AP/LAT)	0.001	0.002	0.001	0.001	0.001	0.001	0.001	0.001	0.209
	CT	0.05								
	DECT			0.05			0.05		0.05	
SoCa*	X-Ray	0.001	0.002	0.001	0.001	0.001	0.001			0.057
	CT	0.05								
Difference Study vs SoCa		0	0	0.05	0	0	0.05	0.001	0.051	0.152

SoCa: Standard of Care; Y: Year; V: Visit; mSv: millisievert; CT: Computed Tomography; DECT: Dual Energy CT scan; IS: Implant Surgery; HD: Hospital discharge; W: week; M: Month

\*SoCa: SoCa of diagnostic, peri-and post-operative management at the CHL supported by the PI and appointed radiologist (see also statement letters supporting the SoCA imaging and radiation exposure letters).

### 1.2.2. Known potential benefits

- **Avoid bone graft harvesting and its related comorbidities**

The use of NVDX3 eliminates the need for an invasive and cumbersome iliac crest harvesting along with its known risks and complications .

- Prolonged intervention time due to the need to perform the graft harvesting.
- Peri- and post-operative complications like injury of the physis, pain, nerve damage, and wound healing complications such as bleeding, hematoma and infection.
- Graft resorption.
- Application/molding challenges.
- Limited availability of autologous bone graft material. NVDX3, in the contrary, is manufactured in a controlled setting, guaranteeing the graft quantities needed to cover the surgical needs.

- **No need to add scaffolds/carriers**

The use of NVDX3 does not require an additional scaffold or carrier (eg. Collagen sponge) and consequently eliminates their associated potential side effects (e.g., hypersensitivity reactions).

- **No need to add bone modulating agents**

Since NVDX3 has the potential to promote osteogenesis the addition of other bone modulating agents, such as BMP and bisphosphonates is not required, eliminating the risk of associated side effects and contraindications.

### 1.2.3. Conclusion risk/benefit assessment

Based on the pre-clinical information, the implant procedure, and the expected osteogenic induction properties of IMP, NVDX3 can be considered to have a beneficial risk/benefit profile for use in human

**For the latest updates on potential risks and benefits linked to NVDX3 refer yourself to the latest version of the Investigator Brochure (IB).**

## 2. OBJECTIVES AND PURPOSE

### 2.1. Objectives

This PoC study will assess the safety and the efficacy of NVDX3 supporting orthotopic ossification in adult patients suffering from a Distal Radius Fracture (DRF).

Primary objective:

- To assess the safety of the NVDX3 implant

Secondary objectives

- To assess the acute and long-term safety of the NVDX3 implant
- To assess the efficacy of the NVDX3 implant radiologically and clinically
- To explore and evaluate new radiological assessment methods for NVDX3

### 2.2. Purpose

The NVDX3-CLN01 study is designed as a first in human PoC aiming at assessing the safety and preliminary efficacy of the NVDX3 implant in an orthotopic bone fusion indication, i.e long bone non-union or DRF.

---

 Orthotopic bone formation refers to the presence of bone formation occurring at a normal place in the body, pertaining to a tissue transplant grafted within existing bone. In this study context, including distal radius fracture, bone formation is induced to fill the bone void induced by the trauma.

## 3. STUDY DESIGN AND ENDPOINTS

### 3.1. Description of the study design

This is a prospective, single arm, monocentric first-in-human PoC study in adult patients, suffering from a distal radius fracture, treated during the surgical intervention with NVDX3, an osteogenic implant from human allogeneic origin.

As per standard of care, patients with DRF are followed up to 3 months post-intervention. In the context of this trial, patient safety and IMP efficacy will be followed up to 12 months post-implant surgery.

At the end of this study, the included patients will be invited to participate in a long-term safety follow-up study for an additional period of 10 years.

### 3.2. Study endpoints

#### Primary Endpoint

Evaluation of all SAEs and NVDX3 related AEs between screening (V1) and 12-months post-IS (V8).

#### Secondary Endpoints

##### **Safety**

1. Description of all acute SAEs and NVDX3 related AEs between screening (V1) and 6 weeks post-IS (V5).
2. Description of all SAEs and NVDX3 related AEs beyond 6 weeks (V5 excluded) until 12 months post-IS
3. Description of Treatment Emergent AEs (TEAEs) for the periods:
  - a. Between screening and week 6 (V5 included)
  - b. Between week 6 (V5 excluded) till month 12 (V8 included)
  - c. Full study duration
4. Description of related and unexpected (S)AEs between inclusion and study completion
5. Description of AE of Special Interest (AESI) between inclusion and study completion
6. Description of lab data and vital signs obtained between inclusion and study completion

## Efficacy

- **Radiological assessments on Computed Tomography data (CT) using the extended Lane and Sandhu Scoring tool (eLSS)**

The following assessments will be performed at 3 and 12-months post-IS compared to HD

1. Evaluation of bone formation status
2. Evaluation of bone union status
3. Evaluation of bone remodeling status
4. Evaluation of Total extended Lane and Sandhu Score

- **Radiological assessments on X-ray Using the eLSS tool**

The following assessments will be performed at HD, 2-, 6-weeks, 3-, 6- and 12-months post-IS compared to the peri-operative x-ray acquisitions

1. Evaluation of bone formation status
2. Evaluation of bone union status
3. Evaluation of bone remodeling status
4. Evaluation of Total extended Lane and Sandhu Score

- **Clinical assessments**

The following assessments will be performed at 2-, 6 weeks, 3-, 6-, and 12-months post-IS compared to HD:

1. Grip strength measure with a hydraulic hand dynamometer
2. Modified Mayo Wrist Score (MMWS): A physician-based scoring evaluating the patients' pain, active flexion/extension arc, grip strength and ability to return to regular employment or activities.
3. PRWE Questionnaire: A patient reported scoring evaluating the patients' wrist pain and disability

NRS-pain, a patient reported scoring evaluating the patients' pain, will be performed at HD, 2-, 6 weeks, 3-, 6-, and 12-months post-IS compared to Screening.

---

 As per imaging requirements Dual energy CT (DECT) acquisitions will be obtained. The DECT acquisition also contains the core data of the "normal" CT, enabling to filter and evaluate CT images separately.

## Exploratory endpoints

## 4. STUDY ENROLLMENT AND WITHDRAWAL

### 4.1. Inclusion criteria

Patients must meet all the inclusion criteria to be eligible to participate in the study:

1. Male or female patients within the age range of  $\geq 18$  years to  $\leq 80$  years.
2. Patient diagnosed with DRF **with confirmed**:
  - a. Classification AO/ATO: C2 and C3 - Intra-articular & multifragmentation.
  - b. Estimated volume of the targeted bone void should not exceed 5cc.
  - c. Availability of diagnostic AP and LAT X-ray or CT scan.
3. Patient can undergo the targeted surgical intervention within 7 days post-DRF diagnosis.
4. Patient fulfills criteria for undergoing a surgical intervention.
5. Patient has understood and accepted to participate in the study according to all study procedures by signing the informed consent.

### 4.2. Exclusion criteria

A patient who meets any of the following criteria will be excluded from participation in this study:

1. Open DRF or closed DRF with increased infection risk.
2. Injury to the median nerve.
3. Previous fracture of the target distal radius.
4. Documented disease limiting mobility and functional assessments (eg. Grip strength test).
5. Dependency on crutches or any comparable walking aids.
6. Patient is overweight, has a BMI  $\geq 35$ .
7. Presence of clinically significant infection at the target implant site or systemic infection.
8. History of allergic reaction or any anticipated hypersensitivity to any of the anticipated:
  - a. Osteosynthesis materials (PEEK plate and screws).
  - b. Anesthetic agents.
  - c. Components of the NVDX3 implant.
9. Presence of any auto-immune disease, with exception of well controlled diabetes type-1 or II, or auto-immune thyroid disorders.
10. Positive serology for human immunodeficiency virus (HIV), HBcAb and/or HBsAg.
11. Presence of an active tumor.
12. Documented metabolic bone disease or any disorder, such as but not limited to high-risk osteoporosis, that could interfere with the bone healing and bone metabolism.

13. Chronic, ongoing, or planned use of medications that might affect bone metabolism or bone quality such as bisphosphonates, steroids, methotrexate, anticoagulants, immunosuppressants or immunotherapy.
14. Excessive smoking, history of chronic alcohol or drug abuse within the 12 months prior to screening.
15. Any history of experimental therapy with another investigational drug within 60 days prior to screening.
16. Pregnant women or women of childbearing potential (WOCBP) not agreeing to use an effective method of birth control during the course of the study. Note: WOCBP including peri-menopausal women who have had a menstrual period within 1 year prior to surgery have to have a negative pregnancy test before entering in the study.
17. Any other psychosocial, mental, and physical condition which, in the opinion of the investigator, could interfere with the trial conduct, the patient's compliance or influence interpretation of the results.
18. Patient with historically elevated radiation exposure levels that could in the opinion of the investigator introduce unacceptable radiation risks for the patient, when being accumulated with the radiological examinations planned in this study.

#### **4.3. Strategy for recruitment and retention**

It is intended to enroll 10 evaluable patients. A patient is considered evaluable once he/she underwent the implant surgery with NVDX3. Non-evaluable patients will be replaced.

No specific recruitment activities are envisioned.

#### **4.4. Participant withdrawal or termination**

##### **4.4.1. Reason for withdrawal or termination**

All patient included will be followed for safety and efficacy assessments throughout the complete duration of the study unless the patient withdraws his/her consent. The patient and/or legal guardian(s) are free to withdraw from participation in the trial at any time without prejudice to their continued care and without any need for justification.

---

 an effective method of birth control is defined as a method which results in a failure rate of less than 1% per year such as combined (oestrogen and progestogen containing) hormonal contraception associated with inhibition of ovulation (oral, intravaginal, transdermal), Progestogen-only hormonal contraception associated with inhibition of ovulation (oral, injectable, implantable), Intrauterine device (IUD), Intrauterine hormone-releasing system (IUS), Bilateral tubal occlusion, Vasectomised partner (provided that partner is the sole sexual partner of the trial participant and that the surgical success of vasectomy has been confirmed), Sexual abstinence

A participant may withdraw from the study at any time at his/her own request or may be withdrawn at any time at the discretion of the investigator for safety, behavioral, compliance, or administrative reasons.

If the participant withdraws consent for disclosure of future information, the sponsor may retain and continue to use any data collected before such a withdrawal of consent.

Participants should be withdrawn from the study if any of the following events occur:

1. Participant develops an illness that would interfere with his/her continued participation.
2. Participant is noncompliant with the study procedures or medications in the opinion of the investigator.
3. Participant takes prohibited concomitant medications (that are not prescribed by the investigator) as defined in this protocol.
4. Participant withdraws his/her consent.
5. There is confirmation of a pregnancy during the study, as evidenced by a positive pregnancy test.
6. The sponsor or a regulatory agency requests withdrawal of the participant.

Note: An eligible study participant who withdraw or was withdrawn from the study will not be replaced

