#### **4.4.2. Handling of participant withdrawals or early termination**

The Investigator should document the primary reason for a patient's premature withdrawal from the trial, in the patient file and in the electronic Case Report Form (eCRF). Every effort must be made to perform the protocol-specified safety follow-up procedures to capture AEs and serious adverse events (SAEs) for the whole duration of the study. Refer to section 6.1.4

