## 6. STUDY SCHEDULE

### 6.1. Schedule of Activities Table

	Screening	Acute safety FU					Long-term safety FU			Early Termination ETV
		V1	V2 	V3	V4	V5	V6	V7	V8	
					W2	W6	M3	M6	M12	
			Implant Surgery IS (Max 7 days after DRF diagnosis)	Hospital Discharge HD	IS+13d ± 2d	IS+42d ± 7d	IS+90d ± 15d	IS+180d ± 30d	IS+360d ± 30d	
Informed consent		x								x 
Eligibility criteria		x								x 
Demography		x								
Medical and concomitant medication history		x								
Index fracture evaluation/classification		x								
Physical examination		x	x	x	x	x	x	x	x	x
Weight/Height (BMI) 		x	x	x	x	x	x	x	x	x
Triplectate 12-Lead ECG			x							x
Vital signs		x	x	x	x	x	x	x	x	x
Inspection of the skin of the affected arm 		x	x	x	x	x	x	x	x	x
Standard safety laboratory 		x		x	x	x	(x)	(x)	(x)	
Serology (HIV, HBV & HBC)		x								
Pregnancy test 		x								x
Implant Surgery (IS)			x 							
Peri-operative IS related information			x							
Grip strength test				x	x	x	x	x	x	x
NRS-pain		x		x	x	x	x	x	x	x
PRWE				x	x	x	x	x	x	x
MMWS				x	x	x	x	x	x	x
Radiological efficacy 	AP/LAT X-ray	x*	x 7*	x*	x*	x*	x*	x*	x	x
	DECT-scan	x* (Normal CT)		x			x		x	
AE/SAE collection			x	x	x	x	x	x	x	x
Concomitant medication			x	x	x	x	x	x	x	x
Concomitant therapy				x	x	x	x	x	x	x

1 In-clinic stay: The patient may be hospitalized before the surgery following to hospital standard of care. The required pre-operative assessments can be done up to 3 days before the surgery.

2 Skin inspection to evaluate potential surgical site infections.

3 At screening, Discharge, V4 and V5: safety laboratory analyses are mandatory. At V6, V7 and V8: Upon occurrence or any suspicion of safety related issues.

4 In women of childbearing potential only: a serum pregnancy test will be performed at Screening and at V8

5 Follow the instructions ad per "NVDX3 handling Manual".

6 To guarantee image quality, all X-rays and CT-scan acquisitions will need to strictly follow the imaging instructions as described per "Imaging Acquisition Manual".

7 AP/LAT X-rays: both after insertion of fixation device, and after insertion of the NVDX3 implant (at the end of the surgery)

8 Height at screening only

9 Informed consent proposing participation to the long-term safety follow-up study (NVDX3-CLNOX)

\* Standard of care image acquisitions for the diagnosis and follow-up of DRF

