## **8.2. Safety Reporting procedures**

### **8.2.1. Time period and frequency for collecting AE/SAE information**

All AEs and SAEs will be collected from the signing of the ICF until the (early) Termination Visit at the time points specified in the Schedule of Activities ([Section 6.1](#)).

Any medical condition that is present at the time of the patient’s screening will be considered as baseline and not reported as an AE. However, if the trial patient’s condition deteriorates at any time during the trial, it will be recorded as an AE.

Changes in the severity of an AE/SAE will be documented to allow an assessment of the duration of the event at each level of severity to be performed. AEs characterized as intermittent require documentation of onset and duration of each episode.

Investigators are not obliged to actively seek AE or SAE in patients after their final discharge from the study. However, if the Principal Investigator learns of any SAE, including a death, at any time after a patient has been discharged from the trial, and he/she considers the event to be reasonably related to NVDX3 or trial participation, the Principal Investigator must promptly notify the Sponsor or designee.

Prompt notification by the investigator to the sponsor of an SAE is essential so that legal obligations and ethical responsibilities towards the safety of participants and the safety of an IMP under clinical investigation are met.

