#### **8.2.3. Follow-up of AE/SAE information**

After the initial AE/SAE report, the investigator is required to proactively follow each participant at subsequent visits/contacts.

All SAEs, and non-serious related AEs (excluding unlike related events) will be followed until resolution, stabilization, the investigator determines that it is no longer clinically significant, the event is otherwise explained, or the participant is lost to follow-up.

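### The protocol gives conflicting end points for AE/SAE follow-up of an implanted patient who leaves early, so part of the 12-month primary safety endpoint may not be actively collected

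*Protocol*

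**What the plan says.** **Who stays in follow-up.** Protocol 4.4.1 opens with "All patient included will be followed for safety and efficacy assessments throughout the complete duration of the study unless the patient withdraws his/her consent". Later in the same section it says "Participants should be withdrawn from the study if any of the following events occur". The list that follows has six items: interfering illness, non-compliance, prohibited medication, withdrawal of consent, pregnancy, and a request by the sponsor or an agency. The section also lets the investigator withdraw a patient at discretion, and withdrawn patients are not replaced.

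**How long events are captured.** Section 4.4.2, on premature withdrawal, asks for every effort to carry out safety follow-up "to capture AEs and serious adverse events (SAEs) for the whole duration of the study" and then points to 6.1.4. Section 8.3 says that implanted patients must be followed for safety over the whole study period. Section 8.2.1 says "All AEs and SAEs will be collected from the signing of the ICF until the (early) Termination Visit" and adds "Investigators are not obliged to actively seek AE or SAE in patients after their final discharge from the study". After discharge, 8.2.1 asks the investigator to notify an SAE only if he or she learns of it and "considers the event to be reasonably related to NVDX3 or trial participation".

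**What is scheduled.** The Schedule of Activities (6.1) has one column headed "Early Termination ETV", which includes AE/SAE collection. Section 6.1.4 describes an end-of-study form with the date, the reason and any contact attempts. It describes no later safety contact.

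**What is analysed.** The primary endpoint (Protocol 3.2, SAP 1.3.1) runs from screening to V8 at 12 months. The Safety Set (SAP 3.2) is everyone treated with NVDX3.

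**The concern.** A site with an implanted patient who meets one of the five other withdrawal events has two incompatible instructions about follow-up. It also has two incompatible instructions about when AE/SAE collection ends. The stricter reading (4.4.2, 8.3) carries collection to month 12. The looser one (8.2.1) ends it at the termination visit.

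If the looser one is followed, the patient still counts in the Safety Set denominator for a 12-month endpoint, but events after leaving are no longer sought. Reported frequencies could then be too low in a first-in-human study whose primary objective is safety. Some grounds for leaving (an interfering illness, or investigator discretion for safety) could themselves be linked to later events. That is a possibility only; the documents give no data on it.

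**Working it through.** There is no stated power or sample-size calculation to reproduce: the study is descriptive and 10 patients were chosen without a formula. The check is therefore a comparison of passages, with simple arithmetic for scale.

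**Step 1: the withdrawal list.** Six items, minus the one that is withdrawal of consent: 6 − 1 = 5 events that conflict with the opening sentence of 4.4.1.

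**Step 2: the rules side by side**, for an implanted patient withdrawn for one of those five events.

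| Place | What it implies |
|---|---|
| 4.4.1, opening | Followed to study end, as consent is not withdrawn |
| 4.4.1, list | Leaves the study |
| 4.4.2 | AE/SAE capture for the whole study |
| 8.3 | Safety follow-up for the whole study period |
| 6.1 and 6.1.4 | One termination visit and a form; no later contact |
| 8.2.1 | Collection ends at that visit; no active seeking afterwards |

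These cannot all be followed. Section 4.4.2 also sends the reader to 6.1.4, which supplies no means of doing what 4.4.2 asks.

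**Step 3: routes for a new event after the termination visit, if 8.2.1 is followed.**

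- SAE related to NVDX3 or to trial participation: not actively sought. It is notified under 8.2.1 if the investigator learns of it.
- Other SAE: not actively sought. Section 8.2.5 requires SAEs to be reported within 24 hours of knowledge regardless of causality, but does not say whether this reaches past early termination.
- Non-serious NVDX3-related AE: not actively sought. If it is an AE of special interest assessed as related, 8.2.5 applies with the same uncertainty. Otherwise no route after termination is stated, since 8.2.4 speaks of events while on trial.

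All three kinds belong to the primary endpoint, and none is actively collected. Section 8.2.3 ("All SAEs, and non-serious related AEs (excluding unlike related events) will be followed until resolution, stabilization") follows up events that have already been reported; it does not find new ones.

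**Step 4: scale.** One patient in 10 whose only event of a given type is missed changes that frequency by 1/10 = 10 percentage points. As an illustration, assume that a patient leaves on the nominal visit day with no contact afterwards. Planned follow-up is 10 × 360 = 3,600 patient-days.

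| Leaves at | Days left to V8 | Share of 3,600 |
|---|---|---|
| V5 (day 42) | 360 − 42 = 318 | 8.8% |
| V6 (day 90) | 360 − 90 = 270 | 7.5% |
| V7 (day 180) | 360 − 180 = 180 | 5.0% |

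These figures are per withdrawn patient. They do not forecast how many will withdraw.

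**Step 5: the analysis windows.** Protocol 9.4.2 and SAP 2.4.1.2 and 4.4.1 end the later phase at V8 or at early termination, whichever is earlier. The primary endpoint and its listing in 9.4.2 have no such cut. The termination date on the form is not defined as either the withdrawal decision or the last safety contact. This matters only if events after termination are in fact captured.

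**The case against.** **The study's duration may mean the patient's own participation.** Section 4.4.2 refers to the termination visit, and 9.4.2 equates study completion with V8 or early termination. On that reading 4.4.2 and 8.2.1 agree. It fits poorly, because 4.4.2 is about patients who have already left, and 8.3 speaks of all implanted patients over the whole study period. The 8.3 sentence does sit among the halting rules, but it states no exception. This reading also leaves the conflict inside 4.4.1 untouched.

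**There are safeguards.** This stands in part. Events up to the termination visit are captured, 8.2.3 follows known events, and 8.2.1 and 8.2.5 provide for SAEs that come to the investigator's knowledge. Consent to the long-term study also appears to be offered at the termination visit (schedule footnote 9; the extracted tables are damaged), and that study runs from the patient's last visit. It needs separate consent, however, and its events would not automatically enter this endpoint.

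**The study is descriptive, and disposition is reported.** SAP 4.6.1 gives patients per visit, study duration and reasons for discontinuation, so a reader will see incomplete follow-up. That discloses the gap but does not recover events. The Safety Monitoring Plan may add procedures; it is not among the documents.

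**Two stronger inferences are not supported.** A reader might infer that SAEs unrelated to NVDX3 have no reporting route at all after early termination. The trial-participation wording in 8.2.1 and the causality-free duty in 8.2.5 rule that out; what is missing is active seeking. A reader might also infer that an event captured after early termination would be counted overall but fall in neither AE phase. That depends on the undefined termination date, and SAP 4.4.1 presents the two phases as a breakdown of the entire period.

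**Conclusion.** The point holds as an inconsistency that should be fixed. Section 4.4.1 contradicts itself for five withdrawal events, and 8.2.1 sets an earlier end to AE/SAE collection than 4.4.2 and 8.3. Followed as written, 8.2.1 leaves new SAEs and new non-serious NVDX3-related AEs between early termination and month 12 without active collection, in patients who remain in the Safety Set.

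The size is unknown. It is nil if nobody leaves early or if 4.4.2 is applied in full, and partly mitigated otherwise. The documents do not show that reported frequencies will be too low, only that they could be. Confidence is medium, because it rests on the plain reading of 4.4.2 and 8.3 and on the unseen Safety Monitoring Plan not already settling the matter.

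**What to change.** Reconcile Protocol 4.4.1, 4.4.2, 6.1.4, 8.2.1 and 8.3 so that one AE/SAE collection window applies to every implanted patient who has not withdrawn consent to data collection. It should run to 12 months after implant surgery, as the primary endpoint already states. Section 6.1.4 should say how patients who have left are contacted for AE/SAE information up to that point. Which withdrawal criteria apply is for the sponsor to reconcile.

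As a minor consequential edit, define the termination date on the end-of-study form. Let the later phase in Protocol 9.4.2 and SAP 2.4.1.2 and 4.4.1 run to 12 months for any events captured after early termination.

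The cost is a protocol amendment, which needs review and approval under 13.2, plus safety contacts with withdrawn patients. SAP 3.6 describes the surgical imaging in the past tense, so the collection part may come too late for anyone already withdrawn. The SAP wording can still be changed, or the change can be described and justified in the clinical study report as SAP section 1 allows.
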